8.2 Sample size determination

The primary outcome will be the average area under the curve (AUC) as determined by the daily VAS scores collected per participant over the course of the trial. Previous studies have demonstrated that a 10 mm change in VAS scores and demonstrated a standard deviation of 20 mm. Using these previously published data as a guide for our sample size estimation, we believe a standardized effect size (i.e., the difference in the AUC VAS score means between the two intervention groups divided by the standard deviation) of 0.5 will be clinically relevant to detect. Furthermore, based on our prior research with endometriosis patients, we anticipate a withdrawal rate of 20%. Therefore, we propose a target sample size of 160 (80 per intervention) randomized participants for this trial. Such a sample size yields 80% statistical power with a two-sided, 0.05 significance level test to detect a standardized effect size of 0.5, while accounting for the 20% withdrawal rate. The true statistical power actually may exceed 80% because our statistical methodology will include partial data for those participants who withdraw (up to the point in time at which they withdraw).

8.3 Statistical methods

The VAS scores will be collected daily from 1-week pre-intervention to 12 weeks postintervention. Prior to analysis, the AUC VAS scores will be calculated per participant separately for the 1-week pre-intervention period and the randomization to 12 weeks post-intervention period. Subsequently, the AUC VAS score data will be normalized per participant to an average AUC VAS score per week (i.e., 7 days) to account for participants that withdraw early from the study. The primary outcome of interest is the AUC VAS scores from randomization to 12 weeks post-intervention period. For this primary outcome, a linear mixed-model will be used to compare the average AUC VAS scores from randomization to 12 weeks post-intervention between the two intervention groups, adjusting for the covariate of opioid intake during the 12-week trial as measured in morphine equivalent units (MEUs)) and using the subject as a random effect in the model.

A secondary analysis with AUC VAS scores as the outcome will use a linear mixed-effects model having intervention group, the repeated factor of time period (1-week pre-intervention and randomization to 12 weeks post-intervention), the interaction of intervention group and time period, and the covariate of opioid intake during the trial as fixed effects and the participant as a random effect. Contrasts will be constructed from this mixed model to compare within and between the intervention groups with respect to AUC VAS scores. Similarly, linear mixed-effects models will be used to compare the two interventions over time with respect to the outcomes of PGIC and EHP30 which are collected at 4-week intervals over the course of the trial. Another secondary analysis will fit a linear random coefficients model to the weekly VAS scores (i.e., not AUC) to generate linear trajectories for each intervention group, adjusting for the covariate of opioid intake. From these trajectories, estimates for the rate of change (i.e., slope) over time in VAS scores will be compared between the two intervention groups. In the event linear trajectories do not fit the data well, higher order polynomials (e.g., quadratic) will be considered to estimate the curve trajectory per intervention.

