3.3 Early Withdrawal of Subjects

3.3.1 Criteria for removal from study

Subjects will be removed from the study for safety reasons. Subjects will be evaluated for potential negative reactions to study medications at each visit. Additionally, subjects will be advised to contact the study team with any new negative symptoms to arrange evaluation.

Additionally, unintended pregnancy during the study period will meet criteria for withdrawal from the study.

Withdraw of consent at any time during the study period will also constitute the withdrawal of study subjects.

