3.3.2 Follow-up for withdrawn subjects

The statistical methods allow for withdraw/screen fails. Subjects will be asked to return the study drug to the site if withdrawn or removed from the study. No other safety follow-up planned.

If the subject is removed from the study for any of the above reasons, she will receive the appropriate treatment based on the decisions of her providing physician team. No further data will be collected on these patients.

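### Section 3.3.2 ends pain data when a woman is removed and 8.3 lets her average to date stand for 12 weeks, with no stated target or check for the primary comparison

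*Combined protocol and SAP*

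**What the plan says.** Section 3.3.1 lists three routes out of the study: safety ("Subjects will be removed from the study for safety reasons"), unintended pregnancy, and withdrawal of consent. Section 3.3.2 treats them alike. It opens its rule with "If the subject is removed from the study for any of the above reasons" and ends it with "No further data will be collected on these patients". On analysis, that section says only "The statistical methods allow for withdraw/screen fails".

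Section 8.3 defines the outcome: "The primary outcome of interest is the AUC VAS scores from randomization to 12 weeks post-intervention period". The AUC is first "normalized per participant to an average AUC VAS score per week (i.e., 7 days) to account for participants that withdraw early from the study". A linear mixed model with a subject random effect and an opioid covariate then compares the groups. Section 8.2 confirms that data up to withdrawal are used and suggests that power may therefore exceed 80%.

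Two secondary analyses touch the same data. The pre/post mixed model uses the same normalised AUC. The random coefficients model uses weekly VAS: "estimates for the rate of change (i.e., slope) over time in VAS scores will be compared between the two intervention groups", and "In the event linear trajectories do not fit the data well, higher order polynomials (e.g., quadratic) will be considered". Neither is presented as a check on the primary result. No section names an analysis population, a target of estimation, a missing-data assumption or a sensitivity analysis for the primary comparison.

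**The concern.** The outcome is labelled a 12-week quantity, but for a woman who leaves it is an average over whatever weeks she gave. The primary period yields one value per woman, so the subject random effect cannot be separated from residual error. It cannot give a short record less weight, and it cannot use her earlier course to inform the unseen weeks.

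The average to date equals the 12-week average in expectation only under conditions that the plan does not state, such as a flat pain profile with withdrawal unrelated to pain. Two departures matter. If benefit builds, leavers contribute mainly early weeks with little benefit. If pain is falling in both arms and more women leave one arm, that arm looks worse for reasons of timing alone.

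Both are plausible here. Women may start or switch to norethindrone only one to two weeks before randomisation and the dose may be adjusted later (3.1, 7.1), so pain may still be changing. Safety is a removal reason, so unequal withdrawal cannot be excluded. Part of the loss is also avoidable: a woman removed for safety or pregnancy may be willing to keep reporting, but 3.3.2 rules that out.

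**Working it through.** **Inputs from 8.2:** difference 10 mm, SD 20 mm, two-sided 0.05, 80 per arm, 20% withdrawal.

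**Plan's own figure.** A two-sample t-test at effect size 10/20 = 0.5 with 80% power needs 63.8, so 64 per arm. 64/0.8 = 80 per arm, 160 in total. This reproduces.

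**Assumptions, not in the documents.** SD 20 mm is that of the 12-week mean. Leavers' last observed week k is spread evenly over weeks 1-11 (mean 6) or weeks 1-4 (mean 2.5). Weekly residual SD is 12 mm in the simulations. The opioid covariate is left out because its relation to pain is not given. Results are shown as weeks 1-11 / weeks 1-4.

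**1. Linear build, equal 20% withdrawal.** The effect in week j is c·j with mean 6.5c = 10, so c = 1.538. A leaver's average to date is c(k+1)/2.
- Weeks 1-11: 1.538 × 3.5 = 5.38, so 0.8 × 10 + 0.2 × 5.38 = 9.08 mm.
- Weeks 1-4: 1.538 × 1.75 = 2.69, so 0.8 × 10 + 0.2 × 2.69 = 8.54 mm.

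Simulated power of the planned comparison is about 81% / 75%. With a constant effect the estimate stays at 10.0 mm and power is 84-89%. With no drug effect there is no bias and type I error is 5%.

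**2. No drug effect, unequal withdrawal.** Suppose pain falls linearly by 20 mm to week 12 in both arms. The 12-week mean fall is 20 × 6.5/12 = 10.83. A leaver's mean fall to date is 20(k+1)/24 = 5.83 / 2.92, so she scores worse by 5.0 / 7.9 mm.

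| Placebo / LDN leaving | Fall | Timing | Spurious difference | Type I error |
|---|---|---|---|---|
| 15% / 25% | 20 mm | weeks 1-11 | 0.10 × 5.0 = 0.5 mm | 5% |
| 10% / 30% | 20 mm | weeks 1-11 | 0.20 × 5.0 = 1.0 mm | 6% |
| 10% / 30% | 30 mm | weeks 1-4 | 0.20 × 11.9 = 2.4 mm | about 11% |

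The shift is against LDN if more leave LDN, and in its favour if more leave placebo. In the 10% / 30% cases a weekly repeated-measures model gave 0.0-0.1 mm and 5%.

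**3. Against the effect regardless of leaving, linear build.** If benefit is lost on leaving, a leaver's 12-week mean effect is the average of c·k(k+1)/24. This is 1.538 × 52/24 = 3.33 / 1.538 × 10/24 = 0.64, so the target is 8 + 0.2 × 3.33 = 8.67 / 8 + 0.2 × 0.64 = 8.13. If a fraction f of the lost benefit is kept, add f × (10 − target).

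| Benefit kept | Target (mm) | Planned minus target (mm) |
|---|---|---|
| none | 8.67 / 8.13 | +0.4 / +0.4 |
| 25% | 9.00 / 8.60 | +0.1 / −0.1 |
| 50% | 9.33 / 9.06 | −0.3 / −0.5 |

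**4. Limits of a weekly model (benefit lost).** With no diaries after removal it estimates 10.0 mm, an error of 1.33 / 1.87. If a share r of removed women keep reporting, the error is (1 − r) times that. It beats the planned method's 0.41 only if r exceeds 1 − 0.41/1.33 = 69% / 1 − 0.41/1.87 = 78%.

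**5. Power for that target.** With complete reporting, SD 20 and 80 per arm, a t-test has about 78% power at 8.67 mm and 72% at 8.13 mm.

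**The case against.** The plan does have a rule for withdrawal, and it can be read as targeting the average while in the study: 8.2 and 8.3 together describe a weekly average up to the point of leaving. For that target, 9.08 and 8.54 mm are the right answers and the planned method has no error. This stands. The dilution in step 1 exists only relative to a hypothetical trial in which nobody left, and should not be called bias in an on-treatment effect. The reading does not remove step 2: a difference caused by unequal timing of departure is not a drug effect, whatever the target is called.

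Against the effect regardless of leaving, the planned method errs by only −0.5 to +0.4 mm under linear build. This also stands. The error is larger if the effect is constant and lost on leaving: 10 − (8 + 2 × 6/12) = +1.0 mm, or 10 − (8 + 2 × 2.5/12) = +1.6 mm. A weekly model without later diaries shares that error.

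A reader might infer that a weekly model assuming data missing at random should replace the primary analysis. Step 4 does not support this: without diaries after removal it can lie further from the regardless-of-leaving target, and the share of removed women who could be followed is unknown because no split of reasons is given.

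The random coefficients model is likelihood-based, and its fitted curves could yield a 12-week average. It is a partial safeguard, but the planned contrast is slope. The falls and imbalances in step 2 are assumed, and norethindrone starts before randomisation, so a fall of 20-30 mm afterwards may not occur.

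**Conclusion.** The point holds in a limited form and should be fixed. The stated rules cause an avoidable loss of data, and they let records of unequal length stand for one 12-week outcome with no named target and no check. Under the assumptions above, the comparison is diluted to about 9.1 or 8.5 mm relative to no withdrawal when benefit builds. With no drug effect it shifts by about 0.5-1.0 mm when withdrawal differs by 10 to 20 points while pain falls 20 mm; 2.4 mm needs a large imbalance, a 30 mm fall and early departure together. With equal withdrawal and a null or constant effect there is no bias against the no-withdrawal average.

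A reader might infer that the primary analysis is invalid or the trial too small. The documents do not support either: 160 reproduces, and no trajectory or withdrawal by arm is given from which size or direction could be fixed. Nor do they support extending the point to women who only stop study drug, since 3.3.1 does not list that as a reason for removal. The remark in 8.2 on power is possible but not assured. Confidence is high on the omission and low on the size of its effect.

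**What to change.** 1. **Section 3.3.2.** Limit the end of data collection to women who withdraw consent. Keep sending the daily VAS and 4-weekly surveys to other removed women who agree, analyse them as randomised, and report withdrawals by arm, week and reason. The daily emailed diary already runs off study drug for four weeks after week 12 (7.2.5), so the system exists.
2. **Section 8.3, target.** State whether the primary comparison targets the effect regardless of stopping treatment, which change 1 supports, or the average while in the study.
3. **Section 8.3, check.** Prespecify, as a check on the primary result, a likelihood-based repeated-measures model of weekly mean VAS (group, week, group by week). Its contrast is the equal-weight average of the 12 weekly differences, and its missing-at-random assumption should be stated. Add one sensitivity analysis for unseen weeks after removal: for example, placebo-arm values for removed LDN women, or a delta-adjusted tipping point. Do not make the weekly model primary for the regardless-of-leaving target without change 1.
4. **Section 8.2.** Qualify the remark that power may exceed 80%.

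The cost is analysis-plan wording, a short protocol amendment, possibly a consent line, and some coordinator follow-up. Data from women who withdraw consent remain lost. The expected difference may be smaller if the target is the effect regardless of leaving (step 5 of the working), and the sponsor should weigh that when choosing.

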3.0 Inclusion and Exclusion Criteria

3.1 Inclusion Criteria

Inclusion

- Premenopausal female ages 18 to 45 years old on the day of signing informed consent.
- Must agree to use only study-specific analgesic medications during the study and is not known to be intolerant to them.
- Diagnosed with endometriosis and has had, within the last 10 years prior to signing the informed consent, surgical diagnosis with direct visualization and/or histopathologic confirmation of endometriosis.
- Is not expected to undergo gynecological surgery or other surgical procedures for treatment of endometriosis during the study period.
- Agrees to use contraception if not surgically sterile during the entire study.
- Patients using oral contraceptives, LARCs and/or GnRH agonists/antagonists for contraception and/or management of endometriosis, with a stable regimen, will be able to continue in the study, however, women using oral contraceptives and GnRH agonist/antagonists will be switched to Norethindrone acetate during the 1-2 week run-in period as prescribed by principle investigator.

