Pre-screening will take place over the phone with women identified as potential candidates for study participation via clinic visits or other previously discussed methods of subject recruitment. Initial contact will be made via the telephone to assess women's interest in participation. As per standard of care, narcotic usage is assessed during routine clinic visits.

If the subject meets all pre-screening criteria, the subject will be scheduled for a screening visit. At the screening visit, the informed consent will be reviewed and the subject will be given ample time to ask any questions or concerns about the study. Once informed consent is signed, the subject information will be placed in redcap and a test email will be sent to the subject. Those meeting all inclusion and exclusion criteria that are willing to participate will receive a detailed past medical history and physical exam. Baseline surveys and any adverse events will be collected and entered into the RedCap secured database.

The subject will complete the WERF survey, VAS score, EHP-30 and PGAs during the visit to ensure understanding and allow the coordinator to help with any questions. The subject will be given a 2 week supply of Norethindrone acetate to start during the run-in period and given instruction on how to complete the daily VAS scores and study questions. It will be explained to the subject that they must complete at least 6 out of the 7 days of surveys to be enrolled into the study. If the subject is unable to complete the 6 out of 7 days of surveys, the subject will be given one additional week to determine if compliance is attainable. (This will ensure provide ample opportunity for

enrollment for potential subjects with unpredictable barriers to completion in the first 7 days.) If the subject is unable to do so, they will be a screen fail. Those completing greater than or equal to 6 entries in either of the 7-day periods will be eligible for enrollment in the study. In the event of needing an additional 7-day run-in period, data points during the screening period will **not** be assessed in aggregate for eligibility.

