7.4.3 Method for Assigning Subject to Treatment Groups

Randomization is a critical feature of a clinical trial because it prevents treatment-selection biases. The statistician involved in this study will develop the programs necessary for the random number generator to create the randomization; however, the final random seeds used to generate the randomization scheme will be prepared by a statistician in PSU's Department of Public Health Sciences independent of the study in order to keep this study's statisticians blinded as well. The randomization scheme for this study will use variable-size, random permuted blocks to ensure that ensure the number of participants in each treatment arm. IDS will be performing randomization to ensure proper blinding of the study team. They will also be responsible for distributing the study medications according to assigned group as per there standard operating procedure.

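### The primary pain analysis omits the run-in VAS score that the plan already calculates, and so gives up precision

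*Combined protocol and SAP*

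**What the plan says.** Section 8.3 (Statistical methods) defines two summaries for each woman: "the AUC VAS scores will be calculated per participant separately for the 1-week pre-intervention period" and for the 12 weeks after randomisation. Both are then put on a per-week scale. For the primary outcome, "a linear mixed-model will be used to compare the average AUC VAS scores from randomization to 12 weeks post-intervention". The only covariate named is opioid intake over the 12 weeks, and the model is fitted "using the subject as a random effect in the model".

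The run-in AUC is used in one place, a secondary model with group, period (run-in or 12-week) and their interaction. There it is one of the two repeated outcomes, not a covariate.

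Three other places bear on the point:

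- Section 7.2.1 makes diary completion a condition of entry: "Those completing greater than or equal to 6 entries in either of the 7-day periods will be eligible for enrollment". Section 7.1 has the same threshold.
- Section 7.4.3 describes the allocation: "The randomization scheme for this study will use variable-size, random permuted blocks". It names no stratification factor.
- Section 3.1 says that "women using oral contraceptives and GnRH agonist/antagonists will be switched to Norethindrone acetate during the 1-2 week run-in period", so hormonal treatment changes for some women during the baseline week.

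**The concern.** Every randomised woman has at least six of seven daily pain scores from the run-in, on the same scale as the primary outcome. Section 8.1 expects half of those screened to fail because of this requirement. The trial pays for a nearly complete baseline and then leaves it out of its main test.

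If run-in pain predicts pain over the following 12 weeks, adjusting for it lowers the residual variance and narrows the confidence interval. It also takes out the part of a chance baseline difference between arms that carries into the outcome. These are two views of the same loss, not two separate losses. Randomisation balances pain on average, but nothing in section 7.4.3 limits the imbalance in a single trial, and section 3.1 sets no minimum VAS score that would narrow the spread of baseline pain.

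The secondary two-period model does not fill the gap. Leaving the opioid term aside, its contrast at the 12-week period is the unadjusted difference, and its interaction is a comparison of changes from baseline. Neither is covariate adjustment, and a secondary result does not alter the primary estimate.

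**Working it through.** **Inputs.** From section 8.2: difference 10 mm, SD 20 mm, standardised effect d = 10/20 = 0.5, a test "with a two-sided, 0.05 significance level test", 80 per arm, 20% withdrawal. Assumed, because no document gives it: r, the correlation between run-in and 12-week AUC, at 0.2, 0.3, 0.5 and 0.7. Also assumed: a baseline SD of 20 mm. Figures in mm are on the mean-daily-VAS scale (weekly AUC divided by 7).

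**The plan's own figure.** A two-sample t-test at d = 0.5 needs 63.8, so 64 per arm. Allowing for withdrawal, 64/(1 − 0.2) = 80 per arm, or 160 in all. Power at 64 per arm is 80.1%, which agrees with the statement "Such a sample size yields 80% statistical power". The sample size therefore rests on a comparison with no baseline adjustment.

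**Adding the baseline.** The residual SD becomes 20·√(1 − r²), the effective effect size 0.5/√(1 − r²), and the degrees of freedom 2n − 3. The 95% CI half-width is t·20·√(1 − r²)·√(2/n). Power is from the noncentral t distribution.

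| r | Residual SD (mm) | Power, 64/arm | Half-width, 64/arm (mm) | n/arm for 80% power | Power, 80/arm |
|---|---|---|---|---|---|
| unadjusted | 20.0 | 80.1% | 7.0 | 64 | 88.2% |
| 0.2 | 19.6 | 81.7% | 6.9 | 62 | 89.4% |
| 0.3 | 19.1 | 83.7% | 6.7 | 59 | 90.9% |
| 0.5 | 17.3 | 90.0% | 6.1 | 49 | 95.2% |
| 0.7 | 14.3 | 97.6% | 5.0 | 34 | 99.3% |

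The column for 80 per arm applies if the partial data of women who withdraw count fully.

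**Against the planned opioid-adjusted model.** For illustration, let opioid intake correlate 0.3 with the outcome and c = 0.15 to 0.3 with baseline, and be unaffected by treatment. The planned model then explains 0.3² = 0.09 of the variance. With baseline added, the share explained is R² = (r² + 0.09 − 2·r·0.3·c)/(1 − c²). At r = 0.5 and c = 0.3 this is (0.25 + 0.09 − 0.09)/0.91 = 0.275. Power follows from 0.5/√(1 − R²):

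| r | Planned model, 64/arm | Baseline added, 64/arm |
|---|---|---|
| 0.2 | 83.7% | 84.2–84.7% |
| 0.3 | 83.7% | 85.6–86.3% |
| 0.5 | 83.7% | 90.9–91.9% |
| 0.7 | 83.7% | 97.7–98.3% |

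**The secondary interaction contrast.** With equal SDs, a change score has variance 2(1 − r) relative to the unadjusted comparison, against 1 − r² for baseline adjustment. At r = 0.3 these are 1.40 and 0.91. Power at 64 per arm is 60.2, 66.0, 80.1 and 95.2% for r = 0.2, 0.3, 0.5 and 0.7. The change score is below baseline adjustment throughout, and below the unadjusted comparison when r is under 0.5.

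**Chance imbalance.** The SE of the baseline difference is 20·√(2/64) = 3.54 mm, or 20·√(2/80) = 3.16 mm. A difference of 5 mm or more in either direction then occurs in 15.7% of trials at 64 per arm and 11.4% at 80. With an assumed slope of 0.2 to 0.7, a 5 mm difference shifts the unadjusted estimate by 0.2 × 5 = 1.0 mm to 0.7 × 5 = 3.5 mm, against the 10 mm target.

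**The subject random effect.** With one primary AUC per woman, the variance of each observation is subject variance plus residual variance. The likelihood depends only on the sum, so the two parts cannot be separated. The treatment estimate equals that from ordinary least squares.

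**The case against.** The strongest reply is that nothing here is an error. The planned test keeps its type I error, 160 reproduces without baseline adjustment, and chance imbalance is random error that the confidence interval already covers. All of this stands, and it is why the point concerns efficiency and not validity.

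The second reply is that the gain may be small, and this also stands. Some women start or switch to norethindrone acetate in the run-in (sections 3.1, 7.1 and 7.2.1), the dose may be adjusted later (section 7.1), and section 2.1 describes the pain as cyclic while the baseline is a single week. Each could lower r. Against the opioid-adjusted illustration the gain at r = 0.2 is only 0.5 to 1 percentage point. If opioid intake correlated 0.5 with baseline pain, it would be about 0.1 point at r = 0.2 and 1.2 points at r = 0.3. The illustration also assumes that treatment does not change opioid use, although section 12.1 lists lower narcotic use as a possible benefit. No power figure is therefore firmly tied to the model as planned.

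Third, the week before intervention would naturally be read as the qualifying week, and the redundant random effect changes no result. Both are matters of wording.

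None of this is a reason to leave the baseline out. The data exist, and at low r almost nothing is lost by including them.

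**Conclusion.** The concern holds. The primary model omits a baseline that the plan collects, nearly completely, and calculates. The consequence is a wider confidence interval than necessary and no correction for chance imbalance in pain. It is not bias, and the sample size is not wrong.

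The size depends on r, which is unknown. Relative to an unadjusted comparison, the variance falls by r²: 4% at r = 0.2, 9% at 0.3, 25% at 0.5 and 49% at 0.7. The benefit is slight at the low end and substantial from about 0.5 upward. Confidence in the size is moderate, because r, the baseline SD and the opioid correlations are all assumed. The omission itself is plain from section 8.3. The change should be made, but the trial does not fail without it.

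**What to change.** Amend section 8.3 before unblinding:

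- Add the weekly-normalised run-in AUC VAS as a fixed covariate in the primary model.
- Fit it as an ordinary linear model (ANCOVA), without the subject random effect.
- State that the qualifying seven-day period is the baseline when a second run-in week is used, and note that these women will have had longer norethindrone acetate exposure at baseline than the others.

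The two-period model can remain as a secondary analysis. Whether opioid intake during the trial should stay as a covariate is a separate question that this change does not settle.

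The cost is one degree of freedom and a few sentences of amendment. No new data are needed and the sample size does not change. Specifying the adjustment in advance also avoids an argument about post hoc adjustment if the arms turn out to differ in baseline pain.
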